After providing informed consent and completing a baseline survey (see section V. A.), participants will be block-randomized in a 2:1 ratio to usual care with (N=200) or without (N=100) LCS navigation. The randomization scheme will be concealed from the study coordinator responsible for randomizing participants. Randomization will be stratified by smoking status (current/former), housing status (homeless/housed), prior discussion of lung cancer screening with their PCP, and primary clinical site where the patient sees their PCP (JYP vs. non-JYP sites) to ensure balance between study arms on these variables. We will stratify by smoking status (determined based on responses to the eligibility screener) because lung cancer risk perceptions and LCS motivations may differ between current and former smokers.^{75,76} Current smoking will be defined as having smoked all or part of a cigarette in the past 30 days.⁷⁷ We will stratify by housing status based on responses to various items within the baseline survey because the navigation needs of formerly homeless people in housing may differ from those who are currently homeless. Current homelessness will be defined in the following ways: a) usually staying in an emergency shelter, transitional shelter, abandoned building, place of business, car or other vehicle, church or mission, hotel or motel, or anywhere outside during the past 7 days, b) usually housed in last 7 days but cannot stay in a residence for at least 14 days, c) usually institutionalized in the last 7 days if the admission was less than 90 days and they were homeless prior to admission, or d) usually institutionalized in the last 7 days if the

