1) *LCS navigation:* The navigator will introduce the concept of LCS and assist participants in scheduling and attending a shared decision-making (SDM) visit with their PCP to discuss the test in greater depth. The navigator will proactively reach out to PCPs about this via electronic messaging through the BHCHP EHR and make him/herself available to assist in the LCS process. If a PCP and a participant jointly decide to pursue LCS, the navigator will assist with booking the LDCT appointment at a local facility that offers this test and interprets it according to the Lung-RADS framework.⁸⁰ BHCHP maintains strong clinical ties with Massachusetts General Hospital, Boston Medical Center, and several other area hospitals, enhancing the feasibility of referring patients to these facilities for LDCT. The navigator will work collaboratively with participants to reduce the barriers to LCS completion while building participants' self-efficacy. If a participant has difficulty obtaining LDCT because of lack of insurance, the navigator will connect the participant with a BHCHP benefits specialist to enroll in health insurance under the state's universal coverage system. Following LDCT, the navigator will coordinate a follow-up appointment with a participant's PCP to discuss the results and arrange any necessary follow-up testing. Throughout this process, the navigator will provide reminder phone calls about upcoming appointments, arrange for transportation assistance and other enabling services when needed, and reinforce the content and concepts covered in the LCS SDM visit through in-person or phone contact. Data from our survey of homeless smokers at BHCHP indicate that over 70% have mobile phones, which will facilitate communication between the navigator and study participants. In addition to documenting their encounters and activities with patients for research data collection purposes (see section VI.A.), the navigator will document within the patients' BHCHP EHR for their care teams to reference as needed.

The navigator will work with each participant for up to 6 months (26 weeks) to receive the initial LCS LDCT scan. If a participant receives their initial LCS LDCT scan within the 6-month (26-week) timeframe and requires follow-up diagnostic testing of abnormal results anytime sooner than the usual LCS LDCT screening interval of 12 months, the navigator will continue to work

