including logistical, physical, or emotional barriers and facilitators. Based on our Health Belief Model framework (Table 2), we will prompt participants to consider the impact of the navigator on a) altering their perceived susceptibility to lung cancer, b) providing them with cues or reminders to pursue LCS, c) enhancing their self-efficacy for pursuing LCS, and d) helping them to overcome barriers to completing LCS. Among participants who undergo LDCT, we will assess their perspectives on the ease of the process, its impact on lung cancer worry, perceived lung cancer risk, and smoking behavior, and the need for any follow-up testing.

PCP interviews: These interviews will elicit PCP perspectives on the challenges of implementing LCS guidelines in primary care practice for a vulnerable population and probe the ways in which the navigator did or did not help to reduce these challenges. We will also seek feedback from PCPs on ways to strengthen the integration of patient navigators into clinical care teams.

B. Study Endpoints

1) Primary outcome: The primary outcome is receipt of LDCT for LCS at 6 months (26 weeks). This will be based on radiology records verifying that a chest CT was performed for LCS and interpreted according to the Lung-RADS framework.⁸⁰ To ascertain this outcome, study staff will examine available health records from BHCHP, MGB, and any other institution for which the participant signs a release of information, as described above in section IV.C. At 6 months (26 weeks) after enrollment, radiology records will be requested/obtained from these facilities. Most Boston-area hospital records are accessible through Care Everywhere in the BHCHP version of Epic and through MGB Epic, supporting the feasibility of gathering this information in an efficient manner. This approach does not rely on participant self-report and therefore does not require in-person or phone follow-up to ascertain. For those verified to have undergone LDCT for LCS within the 6 month (26-week) timeframe, the Lung-RADS result along with any abnormal or incidental findings will be recorded.

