annual screening at 12 months. These individuals will automatically satisfy the secondary outcome. In contrast, Lung-RADS 3-4 findings signal an increased risk for malignancy and merit sooner-than-annual follow-up testing. These individuals will satisfy the secondary outcome only if they obtain the next recommended diagnostic study within 1 month (4 weeks) of the recommended timeframe. For example, if a participant has a Lung-RADS 3 finding for which follow-up LDCT in 6 months is recommended, we will assess whether this follow-up test occurred within 7 months (30 weeks) of the initial LDCT. If a participant has a Lung-RADS 4B/X finding suggesting a high suspicion for malignancy, we will assess whether the recommended follow-up testing occurred within 1 month (4 weeks) of the initial LDCT. The offer of delayed navigation to control arm participants will not interfere with this outcome because a) delayed navigation will be offered only to those who did not undergo an initial LCS LDCT within 6 months (26 weeks) (i.e. the primary outcome), and b) attaining the primary outcome is necessary for satisfying the secondary outcome.

3) Other outcomes: We will examine time to receipt of LDCT for LCS. Process outcomes include acceptance of navigation when offered, number of contacts with the navigator, and attendance of a LCS SDM visit with a BHCHP PCP. Tobacco-related outcomes include receipt of a prescription for any smoking cessation medication and changes in clinically-recorded smoking status (i.e. quitting among current smokers or relapsing among former smokers), both ascertained by BHCHP medical record review. We will track the frequency and types of abnormal findings detected on LCS LDCT, any additional diagnostic testing or therapeutic changes pursued in response to these findings, and the percentage of participants diagnosed with lung cancer (based on radiology and BHCHP and MGB records review). We will also track diagnostic chest CT scans obtained for reasons other than LCS.

C. Statistical Methods

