expected and why the navigation intervention did or did not improve these outcomes. Following from our stratified sampling scheme, we will integrate the quantitative and qualitative data by assessing for thematic differences in the interview content of participants who did (N=20) and did not (N=20) attain the primary outcome. We will focus in particular on comparing and contrasting these two groups' views on the utility of the navigator with respect to the Health Belief Model domains of perceived susceptibility, cues, self-efficacy, and barriers, as described above. We will additionally incorporate the quantitative baseline measures tapping these Health Belief Model domains into integrated analyses. Table 4 illustrates the way in which these quantitative and qualitative data elements will be integrated and presented in a blended fashion.

Table 4. Proposed integration of quantitative and qualitative data.

Health Belief Model domains	Measurement (method)	LCS LDCT at 6 months	
		Yes (N=20)	No (N=20)
Perceived susceptibility / severity	Baseline survey (quan)	Lung cancer risk perception, severity, and worry scores	
	Post-intervention interview (qual)	Quotes/themes about navigator impact on perceived susceptibility/severity	
Cues	Baseline survey (quan)	Past provider recommendation for LCS, exposure to LCS information	
	Post-intervention interview (qual)	Quotes/themes about navigator provision of cues for LCS	
Self-efficacy	Baseline survey (quan)	General and LCS-specific self-efficacy scores	
	Post-intervention interview (qual)	Quotes/themes about navigator impact on self-efficacy	
Perceived benefits / barriers	Baseline survey (quan)	LCS knowledge, competing subsistence difficulty scores	
	Post-intervention interview (qual)	Quotes/themes about navigator assistance with barriers	

D. Power Analysis

The sample size justification is based on the primary outcome of LCS LDCT completion at 6 months (26 weeks). Internal BHCHP data suggests a presently negligible baseline rate of LCS LDCT. Allowing for improvement in this rate as LCS comes into wider practice, we will assume that 5% of usual care (Arm 1) participants will obtain an LDCT within 6 months (26 weeks). In our judgment, increasing this completion rate to 15% would represent a clinically meaningful change. We will have >80% power to detect such a difference with a sample size of 200 in the navigation arm (Arm 2) and 100 in the usual care arm (Arm 1).

VII. RISKS AND DISCOMFORTS

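### Classification of the primary outcome is not masked and the navigator is not kept out of it, although the charts used carry navigator notes for Arm 2 during the 26 weeks

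*Combined protocol and SAP*

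**What the plan says.** **Endpoint.** Section VI.B 1) defines success as a screening LDCT by 26 weeks. Radiology records must establish two things: that the chest CT was done for lung cancer screening (LCS), and that it was read under Lung-RADS. To find this out, "study staff will examine available health records from BHCHP, MGB, and any other institution for which the participant signs a release of information". The secondary outcome in VI.B 2) requires the primary one, so it rests on the same classification.

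**Other CTs.** VI.B 3) adds: "We will also track diagnostic chest CT scans obtained for reasons other than LCS". Someone therefore has to sort chest CTs into screening and non-screening.

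**Navigator notes.** Under LCS navigation in IV.D, besides keeping a research log, "the navigator will document within the patients" own BHCHP records. BHCHP records are also an outcome source. VI.B 2) mentions delayed navigation for control participants, but only for those who had no screening LDCT by 26 weeks. Within the outcome window, then, these notes belong to Arm 2.

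**Masking.** The only concealment stated is in IV.D: the randomization scheme is hidden from the coordinator who randomizes. Nothing is said about masking outcome assessors, a second reader, or a rule for scans of unclear purpose. The navigation log in VI.A describes the person who navigates as study staff, the same term that VI.B 1) uses for those who ascertain the outcome.

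**The concern.** Participants, PCPs and the navigator cannot be blinded to navigation. Outcome classification is where masking is feasible, and the plan does not use it.

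A reviewer who opens a BHCHP chart can learn the arm from the navigator's entries. Those entries may also say where and when a scan was booked, which helps the search in one arm only. If a report is unclear about its purpose or lacks a Lung-RADS category, the reviewer decides with knowledge of the arm and without a written rule.

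The control arm expects few events, so a small number of scans handled differently could change the primary comparison and carry over to the secondary one.

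**Working it through.** **Inputs from the plan.** VI.D gives 5% for Arm 1 and says "increasing this completion rate to 15% would represent a clinically meaningful change" for Arm 2. IV.D has participants "block-randomized in a 2:1 ratio to usual care with (N=200) or without (N=100) LCS navigation". VI.C names the Chi-square test. Alpha and sidedness are not stated; I assume 0.05 two-sided and no dropout.

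**The plan's own figure.** The plan claims more than 80% power.
- Pooled standard error: √(0.11667 × 0.88333 × (1/100 + 1/200)) = 0.0393.
- Unpooled standard error: √(0.05 × 0.95/100 + 0.15 × 0.85/200) = 0.0334.
- Pooled normal power: Φ[(0.10 − 1.96 × 0.0393)/0.0334] = 75.4%. Exact enumeration of the Pearson test gives 76.9%.
- Arcsine gives 80.3%, the likelihood-ratio test 80.4% and unpooled Wald 85.0%.

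The stated power is thus reached by some methods but not by the two-sided Pearson test. That is a separate matter and does not affect this point.

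**Expected events.** 0.15 × 200 = 30 in Arm 2 and 0.05 × 100 = 5 in Arm 1, 35 in all.

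**Scenario A: how many scans change the result?** Suppose 30/200 vs 5/100 is observed and some scans were misclassified in navigation's favour. For the corrected table, z = (p2 − p1)/√(p(1 − p)(1/100 + 1/200)), with p the pooled proportion and no continuity correction.

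| Arm 1 missed | Arm 2 over-counted | Corrected table | z | p |
|---|---|---|---|---|
| 0 | 0 | 30/200 vs 5/100 | 0.100/0.0393 = 2.54 | 0.011 |
| 1 | 0 | 30/200 vs 6/100 | 0.090/0.0398 = 2.26 | 0.024 |
| 2 | 0 | 30/200 vs 7/100 | 0.080/0.0403 = 1.99 | 0.047 |
| 3 | 0 | 30/200 vs 8/100 | 0.070/0.0407 = 1.72 | 0.086 |
| 2 | 1 | 29/200 vs 7/100 | 0.075/0.0398 = 1.88 | 0.060 |
| 2 | 2 | 28/200 vs 7/100 | 0.070/0.0393 = 1.78 | 0.075 |

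No single error, and no two Arm 1 errors, move this table past 0.05. Three errors in the same direction, at least two of them in Arm 1, are enough.

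**Scenario B: false-positive rate with no true effect.** Let the true screening rate be 5% in both arms. Let a be the share of participants with an ambiguous chest CT, and q1 and q2 the fractions of these counted as screening in Arms 1 and 2. Observed rates are 0.05 + a·q1 and 0.05 + a·q2, so the spurious difference is a(q2 − q1). Exact enumeration of the two-sided Pearson test gives:

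| a | q1 = 0.25, q2 = 0.75 | q1 = 0, q2 = 1 |
|---|---|---|
| 1% | 4.6% | 5.1% |
| 2% | 5.1% | 8.0% |
| 3% | 6.2% | 13.2% |
| 5% | 9.6% | 29.1% |
| 10% | 23.9% | 76.9% |

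With arm-neutral coding (q1 = q2 = 0 or 0.5) the rate stays at 4.7–4.9% for a from 1% to 10%. At a = 5% with the 25/75 split, the spurious difference is 0.05 × 0.50 = 2.5 points. The values of a, q1 and q2 are assumptions; the documents give none of them.

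**The case against.** The strongest reply is the endpoint definition. Both conditions must come from radiology records, and a navigator's note is not one. A reader might infer that a note can settle an ambiguous CT as screening in Arm 2. VI.B 1) does not support that: a note cannot supply a Lung-RADS reading, and a scan clearly without one fails in either arm.

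A reader might also infer that only Arm 2 charts document a screening purpose. That too goes beyond the text. VI.A lists shared decision-making visits, CT referrals and CT completion as chart items without restriction by arm, and V.D leaves ordering to PCPs in both arms. Navigated scans follow a joint decision and are booked at Lung-RADS facilities (IV.D), so they may be the least ambiguous. III.A excludes people presenting with symptoms concerning for lung cancer, IV.C seeks record releases from all participants, and collection forms carry prompts (IX.A) that we cannot see.

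All of this stands, and it limits the scope. It does not close the gap. No visible rule covers a mixed indication, a report without an explicit category or an incomplete outside record. Asking everyone for a release does not stop a note from directing the search in one arm. Nor does the definition keep the navigator from acting as assessor.

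**Conclusion.** The point holds as a gap in protection against bias: no masking of classification is planned, the navigator is not excluded, and the arm can be read from a chart used for the outcome. That no masking is planned is read from the plan's silence; the plan does not say that assessors will know the arm.

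Two stronger readings should be set aside. The first is that the error must favour navigation. Extra search information in Arm 2 makes that direction plausible, but the documents do not establish it. The second is that one or two scans would overturn the result: one or two missed Arm 1 scans alone leave p at 0.024 and 0.047.

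The size depends on how many scans are ambiguous. At 1% of participants the effect on the false-positive rate is negligible. At 5% with arm-dependent coding it is 9.6% to 29.1%. These are scenarios, not estimates. The change is worth making because it is cheap and protects both the primary and secondary outcomes.

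**What to change.** In VI.B 1):

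- **Search.** Retrieve all chest CT orders and reports for every participant from the same list of sources over the same 26 weeks. Do not use navigator notes or the navigation log to direct the search.
- **Classify.** Have an existing staff member who neither navigated nor randomized participants, for example the data analyst, classify each chest CT as LCS or non-LCS from the order and radiology report alone. Withhold arm, navigator notes and log. The coordinator who randomizes cannot fill this role. IX.A may give the analyst routine access to study data, so the assessor should have no access to allocation until classification is complete.
- **Code.** Fix in advance one arm-neutral rule for an unclear indication or a missing Lung-RADS category.
- **Test.** Run a sensitivity analysis, identical in both arms, that codes all ambiguous scans as LCS and then all as non-LCS. An analysis dropping only Arm 2 scans located through navigator notes should not be used, because it would remove radiology-verified events from one arm only.

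**Cost.** Protocol wording, a redacted extract, and a few hours of existing staff time for about 35 expected screening scans plus the diagnostic CTs. A report may occasionally reveal the arm. The source list must be broad, since a scan outside it would no longer be found through a note.

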Mitigating disparities in lung cancer outcomes and fully realizing the potential benefits of LCS among homeless people will require thoughtful interventions deployed through the clinical programs that serve this vulnerable population. Patient navigation, a strategy for guiding individuals through complex health systems,³⁹ may be a promising approach for helping homeless people overcome their unique barriers to LCS.⁴⁰ Navigation interventions have been shown to improve cancer screening participation^{36,37,41-56} and diagnostic resolution of abnormal results⁵⁷⁻⁶³ in vulnerable populations. Patient navigation has been endorsed by the ACS⁶⁴ and the National Cancer Institute⁶⁵ as a valuable approach to reducing cancer health disparities,⁶⁵ but this approach has not been tested rigorously in a homeless health care setting. Our research group is well-poised to conduct such a study by leveraging our extensive clinical and research experience with this population and our 9-year partnership with BHCHP, an internationally-renowned organization that serves over 12,000 currently (84%) and formerly (16%) homeless people annually through dozens of clinical sites in greater Boston.⁶⁶ This innovative community partnership has given rise to numerous impactful studies on the health of homeless-experienced people,^{2,5,6,33-35,67} including a recently pilot trial for homeless smokers that had brisk recruitment, high retention rates, and encouraging results (NCT02565381).

II. SPECIFIC AIMS

Aim 1: To determine the effect of patient navigation, added to usual care, on 1°) LCS LDCT completion at 6 months (26 weeks) and 2°) LCS LDCT completion at 6 months (26 weeks) and diagnostic follow-up of abnormal results within 1 month (4 weeks) of the recommended timeframe, among homeless-experienced people who are eligible for LCS.

Hypothesis: Participants assigned to receive patient navigation will have significantly greater 1°) LCS LDCT completion at 6 months (26 weeks) and 2°) LCS LDCT completion at 6 months (26 weeks) with timely diagnostic follow-up of abnormal results.

Aim 2. To conduct post-intervention qualitative interviews of trial participants and BHCHP PCPs to explain and interpret the quantitative findings of the pragmatic clinical trial.

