In order to ascertain the primary and secondary study outcomes of LDCT completion and LDCT completion with timely diagnostic follow-up (see section VII.B.), we will review BHCHP and MGB records for LDCT results in addition to obtaining written authorization from all enrolled participants to obtain their health/medical records for the 14 months following their trial enrollment date from other Boston-area hospitals and health care facilities using a HIPAA-compliant Release of Information (ROI) form which has been vetted by privacy officers at BHCHP, Boston Medical Center, and MGH (Appendix N). Participants who provide verbal consent during an in-person enrollment appointment will also complete the ROI form in person. Participants with a stable home address who complete the enrollment appointment remotely will be given the option to receive a pre-stamped envelope with the ROI form to have them sign and return back by mail to our MGH or BHCHP office.

If COVID-19 prompts further restrictions around in-person research activities at BHCHP, the research coordinator will transition to completing the verbal consent process over the phone or via the HIPAA compliant video conferencing platforms, Microsoft Teams or Enterprise Zoom depending on each participant's preference and access to technology. Based on feedback from the Boston Medical Center Compliance and Privacy Office, obtaining participant medical records for research purposes will continue to require written authorization regardless of current restrictions. Therefore, as noted previously, the research coordinator will offer participants with a stable home address the option to receive a pre-stamped envelope with the ROI form to sign and mail back. For participants who cannot receive a mailed ROI form, we will need to wait until in-person research restrictions are lifted. In this circumstance, once safe to do so, a research coordinator will either directly contact these research participants by phone or attempt to meet them in person at a clinic site to complete the form in person.

D. Treatment assignment

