2) Secondary outcome: Increasing LDCT completion will only reduce lung cancer mortality if individuals with abnormal results can undergo evaluation and treatment of early stage lung cancer in a timely fashion. In the setting of homelessness, a valid concern is whether participants with abnormal LDCT results can be recalled for diagnostic follow-up in a timely manner. To address this concern, our secondary outcome is receipt of LDCT with timely diagnostic follow-up of any abnormal results. To

satisfy this composite outcome, participants must achieve the primary outcome (LDCT at 6 months (26 weeks) and, if the result is abnormal, also obtain the next recommended follow-up

Table 3. Lung-RADS categories.

Category	Description	Management	Malignancy probability	Gen. pop. prevalence
1	Negative	Repeat LDCT 12 mos	<1%	90%
2	Benign			
3	Probably benign	Repeat LDCT 6 mos	1-2%	5%
4A	Suspicious	Repeat LDCT 3 mos +/- PET/CT	5-15%	2%
4B/X		Chest CT, PET/CT, +/- biopsy	>15%	2%

*Adapted from the American College of Radiology

test within 1 month (4 weeks) of the advised timeframe, based on the Lung-RADS framework.⁸⁰ Lung-RADS category descriptions, recommended follow-up, associated probabilities of malignancy, and estimated general population prevalences are shown in Table 3.¹⁰⁴ As described above, we will obtain radiology records for participants who underwent LDCT for LCS to document the findings of the study, determine the Lung-RADS category associated with those findings, and ascertain the recommended diagnostic follow-up plan. Participants with Lung-RADS 1-2 findings do not require specific diagnostic action, but rather may continue with

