Quantitative analysis: LDCT completion at 6 months (26 weeks) (1° outcome) and LDCT completion with timely diagnostic follow-up (2° outcome) are both binary outcomes. In the principal analysis, we will assess the difference between the navigation and usual care arms on attainment of these outcomes using the Chi-square test. We will also use logistic regression models to examine the associations between treatment condition and outcomes including clinical site and other known predictors of outcomes to increase the precision of effect estimates. Additional analyses will examine time to receipt of LDCT for LCS between study arms using time-to-event methods (log-rank tests and Cox regression models). Although we expect to be underpowered to detect significant interactions, we will examine whether the effect of navigation varies by smoking status, housing status, or clinical site in an exploratory analysis.

Qualitative analysis: Qualitative interviews will be audiotaped and transcribed. We will use inductive content analysis methods to identify major and minor themes, and we will use deductive methods to strengthen, refine, and enhance understanding of identified themes.¹⁰⁵ Qualitative data coding will be performed by 2 trained study staff members using NVivo 11 software. The data coders will meet regularly with Drs. [name] and [name] to discuss the structural thematic framework, categories, and coding plan. We will resolve discrepancies through discussion and comparison to raw data. Coding will continue iteratively until a high level of reliability ($Kappa>0.80$) is established.

Integration with quantitative data: Based on a mixed methods approach,¹⁰⁶ we will use the qualitative interview data to interpret and explain the quantitative observations from the trial. This will aid in better understanding why overall LDCT completion was higher or lower than

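### Does the secondary composite leave the plan's question about recall after an abnormal scan unanswered?

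*Combined protocol and SAP*

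**What the plan says.** Section VI.B, Secondary outcome, gives the motive: "a valid concern is whether participants with abnormal LDCT results can be recalled for diagnostic follow-up in a timely manner". It continues: "To address this concern, our secondary outcome is receipt of LDCT with timely diagnostic follow-up of any abnormal results". It then defines the outcome as a composite. A participant must have the initial LDCT by 26 weeks and, if the scan is Lung-RADS 3-4, must also have the next recommended test no later than 4 weeks after the recommended time. Of Lung-RADS 1-2 completers it says "These individuals will automatically satisfy the secondary outcome". Participants who are never screened fail.

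Section VI.C plans to assess "the difference between the navigation and usual care arms on attainment of these outcomes using the Chi-square test", supported by logistic regression. Nothing in VI.C is restricted to abnormal scans.

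Four other places bear on the point:
- The section II hypothesis for the secondary outcome is greater "LCS LDCT completion at 6 months (26 weeks) with timely diagnostic follow-up of abnormal results", which is the composite itself.
- Section VI.B, Primary outcome, records the Lung-RADS result for every verified completer.
- Section VI.B, Other outcomes, states "We will track the frequency and types of abnormal findings detected on LCS LDCT", and also follows the testing those findings led to.
- Section IV.C seeks authorisation for "their health/medical records for the 14 months following their trial enrollment date" from outside facilities.

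**The concern.** The question is about people with abnormal scans, so one expects a denominator of people with abnormal scans. The plan uses everyone randomised. If few scans are abnormal, the composite nearly duplicates the primary outcome, and its between-arm test mostly reflects LDCT uptake. A significant result could then be read as evidence that abnormal results are chased up in time when the data hardly address this. Conversely, an effect of navigation on recall alone would be almost invisible. With no named proportion, the direct answer would have to be worked out after the results were known.

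**Working it through.** **Inputs.** Completion is 5% in usual care and 15% with navigation (VI.D). Arm sizes are 100 and 200 (IV.D). The abnormal share *a* is 5% + 2% + 2% = 9% from Table 3. Those are general-population figures, so 15%, 20% and 30% are tried as assumptions for this older, heavy-smoking group. No alpha is stated; two-sided 0.05 is assumed. The test is the Pearson chi-square without continuity correction, with power by exact enumeration of both binomials.

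**The plan's own figure.** VI.D states power above 80% for the primary outcome. The planned test gives 76.9% (75.4% by the pooled normal formula). Arcsine and unpooled formulas give 80.3% and 85.0%. The argument below does not depend on this gap; 76.9% is the reference.

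**Composite rate in an arm** = completion × (1 − *a* + *a* × *f*), where *f* is the share of abnormal scans followed up in time. For navigation at *a* = 9%: *f* = 1 gives 15%; *f* = 0 gives 0.15 × 0.91 = 13.65%.

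**Chance of a significant composite, with *f* = 1 in usual care:**

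| Abnormal share | Navigation *f* = 0 | Navigation *f* = 0.5 |
|---|---|---|
| 9% | 66% | 72% |
| 15% | 57% | 68% |
| 20% | 49% | 64% |
| 30% | 34% | 57% |

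At 9% the test is insensitive to recall. At 20% to 30%, complete failure of recall costs 28 to 43 percentage points of power (77 − 49; 77 − 34).

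**Expected counts.** Take 30 vs 5 completers with no failures in usual care.
- 30/200 vs 5/100: p = 0.011.
- Five missed abnormal scans, 25/200 vs 5/100: p = 0.041.
- Six missed, 24/200 vs 5/100: p = 0.053.
- All abnormal scans missed at 30% abnormal (30 × 0.30 = 9), 21/200 vs 5/100: p = 0.11.

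Thirty completers include at most five abnormal scans with probability 95% at 9% abnormal, 71% at 15%, 43% at 20% and 8% at 30%. So a significant composite is compatible with anything from no recall to full recall only if the abnormal share is low.

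**Recall effect alone.** With 15% completion in both arms, and timely follow-up of 0% in usual care and 100% with navigation at 9% abnormal, the rates are 13.65% vs 15%. Power is about 6%, close to alpha.

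**What a direct estimate would hold.** Expected abnormal scans at 9%: 200 × 0.15 × 0.09 = 2.7 with navigation and 100 × 0.05 × 0.09 = 0.45 in usual care. The chance of none in usual care is (1 − 0.0045)^100 = 64%. Exact 95% intervals: 0/3 is 0% to 71%; 3/3 is 29% to 100%. At 20% abnormal about 6 vs 1 are expected; 0/6 is 0% to 46%.

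**Is the estimate already determined?** Denominator: Lung-RADS 3-4 initial scans, defined in VI.B. Numerator: next recommended test within the VI.B window, judged participant by participant. Primary minus secondary successes gives the failures in each arm. The longest window closes 26 + 30 = 56 weeks after enrolment, about 13 months, inside the 14 months of records.

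**The case for a change.** The strongest case for a change is that the plan raises a specific question, says the secondary outcome addresses it, and then names no estimate of it. The test can be positive when every recall in the navigation arm fails, and is nearly blind when navigation improves recall alone. Tracking abnormal findings is not a commitment to a proportion, a denominator or a timeliness rule. The remedy is cheap: a sentence or two and a small table, with no new data. Imprecision is itself a reason to show the counts, so that nobody reads recall into a composite p-value.

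Much of this stands. The calculations are right, and neither VI.B nor VI.C names the proportion. Three parts do not carry through. First, the plan never says a significant composite shows better recall; its hypothesis is completion net of failed follow-up, and that is what it tests. Second, the denominator and the timeliness rule are fixed by the composite's own definition, so little is left to choose after the results are known. Third, complete failure with navigation beside perfect recall in usual care is an extreme case, since section IV.D has navigators continue through diagnostic follow-up unless the participant declines. At 50% timely with navigation and 9% abnormal, power is 72% against 77%.

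**Conclusion.** No change is needed. The composite keeps all randomised participants in the comparison, falls when follow-up fails, and is the outcome named in the hypothesis. A between-arm comparison among abnormal scans alone would condition on an event after randomisation and would have about 2.7 vs 0.45 participants at 9% abnormal.

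What is missing is a descriptive line that the existing definitions and data already determine: how many participants had a Lung-RADS 3-4 scan, and how many of them were followed up in time. A competent analyst would tabulate this with the tracked abnormal findings, and no planned test or estimate would move.

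The view that the composite says little about recall rests on the 9% share from Table 3, the planning completion rates and a two-sided 0.05 level. If the true share is 20% to 30%, the composite responds materially to failed follow-up. In either case its p-value should be read as evidence on adequately completed screening, not on recall by itself.
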